Appendix 12: Protocol Amendment History

This document (dated 22 May 2020) is Amendment 1, the document history is below. The Summary of Changes for each amendment listed below will be provided separately.

DOCUMENT HISTORY	
Document	Date
Amendment 1	22-May-2020
Original	26-Feb-2020

1. INTRODUCTION

This statistical analysis plan (SAP) document outlines the statistical methods to be implemented during the analyses of Study Protocol TERN101-2001. The purpose of this plan is to provide specific guidelines from which the analyses will proceed. Any deviations from these guidelines will be documented in the clinical study report (CSR).

This SAP supersedes the statistical considerations identified in the protocol; where considerations are substantially different, they are identified in [Section 11](#). Any post-hoc or unplanned analyses, or significant changes from the planned analysis in this SAP performed to provide results for inclusion in the CSR but not included in this SAP, will be clearly identified in the CSR. Changes to planned analyses do not require an updated SAP but will be included in the CSR if significant.

2. INFORMATION FROM THE STUDY PROTOCOL

2.1. Study Objectives

Primary Objective:

- To evaluate safety and tolerability of 3 doses of orally administered TERN-101 versus placebo for 12 weeks in non-cirrhotic presumed NASH patients, with clinical or histological NASH diagnosis

Secondary Objectives:

- To evaluate the change in alanine aminotransferase (ALT) with 3 doses of TERN-101 for 12 weeks versus placebo in non-cirrhotic presumed NASH patients
- To evaluate the pharmacokinetics (PK) of 3 doses of TERN-101 in non-cirrhotic presumed NASH patients

Exploratory Objectives:

- To assess the effect of 3 doses of TERN-101 on liver fat content (LFC) and additional indicators of NASH disease activity
- To evaluate farnesoid X receptor (FXR) target engagement of 3 doses of TERN-101 in non-cirrhotic presumed NASH patients
- To evaluate the effect of 3 doses of TERN-101 on biomarkers of liver fibrosis

[figure not shown]
2.2. Study Design

This study is a randomized, double-blind, placebo-controlled, parallel-group, Phase 2a study to evaluate the safety, tolerability, efficacy, and PK of various doses of TERN-101 in non-cirrhotic presumed non-alcoholic steatohepatitis (NASH) patients. TERN-101 is a highly selective and potent small molecule agonist of farnesoid X receptor (FXR) in development for the treatment of patients with NASH, a serious and advanced form of non-alcoholic fatty liver disease (NAFLD). The study aims to characterize the effects of varying doses of TERN-101 in a NAFLD patient

population with presumed NASH. Currently, there are no approved therapies for the treatment of NASH.

Figure 1 describes the overall study design. The total study duration will be approximately 24 weeks, consisting of an 8-week Screening Period, a 12-week Treatment Period and a 4-week Follow-up Period.

Figure 1: Overall Study Design

Abbreviations: MRI-PDFF = magnetic resonance imaging proton density fat fraction; PK/PD = pharmacokinetics/pharmacodynamics; QD = once a day

Of the approximately 96 patients randomized, 24 patients will take part in an intensive PK and pharmacodynamic (PD) collection after the first dose and after the last dose of study drug. This includes 6 patients at each TERN-101 dose level, and 6 patients in the placebo group. Patients who are not participating in the PK/PD sub-study will have trough PK/PD sampling only.

2.2.1. Study Procedures

The overall schedule of activities is outlined in Section 1.3 of the study protocol. See study protocol for complete details.

2.2.2. Study Population

This study includes non-cirrhotic presumed NASH patients. Inclusion and exclusion criteria are provided in Sections 5.1 and 5.2, respectively, of the study protocol.

2.2.3. Study Drug

Study drug is defined as any investigational intervention(s), marketed product(s), or placebo intended to be administered to a study patient according to the study protocol.

Table 1: Study Drug

| | | |
|------------|------------|------------|
| [REDACTED] | [REDACTED] | [REDACTED] |
| [REDACTED] | | |
| [REDACTED] | | |
| [REDACTED] | [REDACTED] | [REDACTED] |

2.2.4. Treatment Assignment, Blinding, and Randomization Methodology

Patients will be randomized to TERN-101 or placebo using an Interactive Web Response System (IWRS). Approximately 96 patients will be randomized at an overall ratio of 1:1:1:1 into 4 groups receiving 5 mg (n = 24), 10 mg (n = 24), 15 mg (n = 24) TERN-101 tablet, or matching placebo (n = 24). Randomization will ensure 6 patients at each TERN-101 dose level and 6 patients in the placebo group are assigned to the PK/PD sub-study.

Investigators, patients, all study personnel, and the Sponsor will remain blinded to each patient's assigned dose group throughout the course of the study. The randomization codes will be provided to bioanalytics to allow for the exclusion of placebo patients from the PK assay.

Bioanalytics will not disclose the randomization code or the results of their measurements until the trial is officially unblinded.

Emergency unblinding procedures are outlined in Section 6.4.1 of the study protocol and in the unblinding plan.

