8. EFFICACY ANALYSES

8.1. Adjustments for Covariates

For comparison of treatment groups with respect to change and percent change from baseline, analysis of covariance (ANCOVA)

will be used. The corresponding baseline value will be used as a covariate in the model.

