8.3. Interim Analyses and Data Monitoring

8.4. Multicenter Studies

The randomization is not stratified by site. Likewise, analyses of data will not be stratified by study site.

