8.6. Multiple Comparisons/Multiplicity

There will be no adjustment for multiplicity. Statistical testing will be considered nominal, descriptive, and exploratory.

8.7. Secondary Efficacy Analyses: Percent Change from Baseline in ALT Levels at Week 12

Descriptive statistics of ALT values, change from baseline, and percent change from baseline values will be presented by treatment group for each visit using the Efficacy Analysis Set. In addition, figures of mean (\pm SD) ALT values, change from baseline, and percent change from baseline will be presented over time by treatment group.

Analyses of percent change (and separately change) from baseline will be carried out using an ANCOVA model at Week 12 with percent change (and separately change) from baseline as the dependent variable including treatment group as a fixed effect and baseline as a covariate. The primary analysis of percent change (and separately change) in ALT at Week 12 will be carried out using available observed data only, without imputation for missing data.

The estimates of least-square (LS) means, standard errors (SE), and 90% and 95% CIs will be presented by treatment group. Estimates of the LS mean difference between pooled TERN-101 (All TERN-101) and placebo, and each pairwise comparison between placebo and each active dose of TERN-101, will be presented with the associated standard error of the difference, and 90% and 95% CIs of the difference.

The same ANCOVA model will be used to analyze the last on-treatment value for Week 12, to be labelled as “End of Treatment”. For patients who complete Week 12, the Week 12 value will be used. For patients who do not complete treatment, the last value on treatment will be used.

The same ANCOVA model will be presented for each post-baseline visit using observed data only.

The distribution of percent change values will be evaluated visually for normality assumptions. If normality assumptions are violated, i.e. data are not normally distributed, a Wilcoxon Rank Sum Test will be used to compare each TERN-101 dose to placebo, and pooled TERN-101 (All TERN-101) to placebo. The median differences and 90% and 95% CIs of the median differences between treatment groups will be constructed using Hodges-Lehmann estimate.

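### Sub-study membership is balanced across arms by the randomization but absent from the Section 8.7 ANCOVA; if it predicts outcome beyond baseline, the efficacy intervals are slightly conservative, and the remedy costs one degree of freedom.

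*SAP*

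**What the plan says.** On allocation, SAP 2.2.4 says "Approximately 96 patients will be randomized at an overall ratio of 1:1:1:1 into 4 groups", with 24 patients in each, and adds that "Randomization will ensure 6 patients at each TERN-101 dose level and 6 patients in the placebo group are assigned to the PK/PD sub-study". Protocol 6.4 contains the same rule. SAP 2.2 gives the total: "Of the approximately 96 patients randomized, 24 patients will take part in an intensive PK and pharmacodynamic (PD) collection". Neither document calls sub-study membership a stratification factor.

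On the model, SAP 8.7 specifies an ANCOVA for Week 12 ALT with percent change (and separately change) "as the dependent variable including treatment group as a fixed effect and baseline as a covariate". SAP 8.1 adds that "The corresponding baseline value will be used as a covariate in the model" and names no other covariate in its visible text. The 8.7 model is carried into liver fat (8.8.1.1), AST and GGT (8.8.2) and the NASH and fibrosis biomarkers (8.8.3).

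The only statement linking design to analysis concerns centers. SAP 8.4 reads: "The randomization is not stratified by site. Likewise, analyses of data will not be stratified by study site". No visible section puts sub-study membership in an efficacy model or explains leaving it out.

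**The concern.** Holding a factor at the same split in every arm removes its contribution from the real sampling variance of the arm differences. If the factor predicts outcome and is left out of the model, its variance goes into the residual. The standard error then describes a less precise experiment than the one performed.

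The estimate is not biased and false positives do not increase. What is at stake is interval width. Protocol 9.2 sets the sample size on feasibility rather than power, so the width of the intervals is the practical measure of what 24 patients per arm can show on ALT and liver fat.

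**Working it through.** The visible text gives no power figure, standard deviation or expected interval width, so there is no planned figure to reproduce. The counts agree: 4 × 24 = 96 patients, 4 × 6 = 24 in the sub-study, and 24 − 6 = 18 per arm outside it. The 18 is a subtraction from an approximate total; only the 6 is guaranteed.

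**Inputs**
- From the documents: four arms of 24, 6 sub-study patients in each, a model with treatment and baseline, and two-sided 95% intervals.
- Assumed: residual SD of 1; complete data; and a difference d between sub-study and other patients, in residual SDs after baseline adjustment and the same in every arm. The documents give no d, so a range is shown.

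**Formulas**
1. Within an arm, the membership indicator has sum of squares 6 × 18 / 24 = 4.5. Over four arms this is 18.
2. Without the term, the residual degrees of freedom are 96 − 5 = 91, and the expected residual mean square is 1 + 18d²/91.
3. The true variance of a dose-versus-placebo difference is 2/24 for any d, because the 6/18 split is equal in both arms.
4. The half-width without the term is t(0.975; 91) × √[(1 + 18d²/91) × 2/24].
5. The half-width with the term is t(0.975; 90) × √(2/24) = 0.5735.

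For example, at d = 0.5 the mean square is 1 + 18 × 0.25/91 = 1.0495, the half-width without the term is 0.5874, and 0.5874/0.5735 = 1.024.

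| d | Mean square | Half-width without | Half-width with | Ratio | Approx. coverage without |
|---|---|---|---|---|---|
| 0 | 1.0000 | 0.5734 | 0.5735 | 0.9999 | 95.0% |
| 0.25 | 1.0124 | 0.5770 | 0.5735 | 1.006 | 95.1% |
| 0.5 | 1.0495 | 0.5874 | 0.5735 | 1.024 | 95.5% |
| 0.75 | 1.1113 | 0.6045 | 0.5735 | 1.054 | 96.1% |
| 1.0 | 1.1978 | 0.6276 | 0.5735 | 1.094 | 96.8% |

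The lost degree of freedom is repaid once d exceeds √{[(t₉₀/t₉₁)² − 1] × 91/18}, which is about 0.04.

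**Simulation check** (5,000 trials per setting, with a baseline covariate)
- Width ratios at d = 0.25, 0.5 and 1.0 were 1.006, 1.024 and 1.094. The mean error of the estimate was within 0.004 of zero.
- Coverage without the term was 94.9%, 95.1% and 96.9%. The simulation error is about 0.3 percentage points (√[0.95 × 0.05/5,000]), so over-coverage is not distinguishable from nominal at d = 0.5 or below and is clear at d = 1.0.
- With an assumed 15% of outcomes missing at random, the ratio at d = 1.0 was 1.092 and coverage 96.3%.
- With 24 sub-study patients but no balance across arms, coverage at d = 1.0 was 95.4%. The unadjusted interval was then honest, because the estimate really was more variable (SD 0.312 against 0.290). The over-coverage therefore comes from the fixed 6 per arm.
- When the two groups differed by 1 SD in baseline only, the ratio was 0.999 and coverage 94.9%. The baseline covariate already absorbs that kind of difference.

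**The case against.** The strongest reply is that d may well be zero. Both documents say the randomization itself settles who is in the sub-study, and SAP 7.1 counts patients as randomized to it. Read literally, membership is then a random label, the two groups differ only by chance, and the ANCOVA intervals have nominal coverage. Nothing visible says that participants volunteer or come from selected sites. The extra sampling visits make selection by willingness or site capability conceivable, but that is inference. This objection stands, and it is why the point is conditional.

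Three further replies also stand.
- The larger figures need d of 0.75 to 1.0, which has no source in the documents. At 0.5 or below the excess width is under 3%.
- SAP 8.6 labels the tests nominal and exploratory, and the primary endpoint is descriptive safety, so no confirmatory claim depends on this.
- SAP 8.4 speaks of site only. It shows the sponsor relating analysis to design, but it does not commit the plan to a sub-study term.

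These replies do not remove the fact that a factor balanced by design is absent from a fully stated model, or that including it costs almost nothing if d is zero.

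**Conclusion.** The point holds as a minor, conditional one. The randomization balances sub-study membership and the Section 8.7 ANCOVA omits it. If membership predicts outcome beyond baseline, dose-versus-placebo intervals are conservative by about 0.6% at d = 0.25, 2.4% at 0.5, 5.4% at 0.75 and 9.4% at 1.0. If membership is a random label, there is no effect. The figures assume full arms of 24 and the same d in every arm.

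A reader might infer more than this. The documents do not support the following readings:
- **That the intervals in this trial are too wide.** That needs a non-zero d, which nothing in the documents supplies.
- **That any difference between the two groups widens them.** A difference in baseline value alone does not.
- **That the treatment comparisons are biased or produce too many false positives.** Estimates are unbiased and any error in coverage is conservative.
- **That every efficacy model shares the omission.** The MMRM terms in 8.7.1.1 are redacted and text is missing in 8.1, so the finding rests on the ANCOVA written out in 8.7.

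**What to change.** In SAP 8.7, add PK/PD sub-study participation (yes/no) as a fixed effect in the ANCOVA for ALT. Apply it also to the full-sample analyses that reuse that model: liver fat (8.8.1.1), AST and GGT (8.8.2), and the NASH and fibrosis biomarkers (8.8.3). State in 2.2.4 how sub-study patients are chosen. If the sponsor prefers to leave the term out, one sentence giving the reason would do.

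Limits of the change:
- Add the term to the MMRM only if the redacted specification lacks it.
- Do not require it for cT1, which is collected only at capable sites, so the 6/18 split need not hold and sub-study cells may be sparse.
- Do not require it for the Wilcoxon and Hodges-Lehmann fallback or the chi-square responder tests, which carry no covariates as specified.
- Do not extend it to a pre-dose 7αC4 model; SAP 8.10.3 defines none separately.

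The cost is one phrase and 1 of about 91 residual degrees of freedom. If d is zero, the intervals widen by roughly 0.01% to 0.03%.

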2.3. Study Endpoints

2.3.1. Primary Endpoints

[figure not shown]
The primary endpoints are the patient incidence of treatment emergent adverse events (TEAEs), defined in [Section 9.2](#), and patient incidence of treatment emergent clinical safety laboratory abnormalities, defined in [Section 9.3.1](#).

2.3.2. Secondary Endpoints

- Percent change from baseline in ALT levels at Week 12
- Plasma PK for TERN-101 and its main metabolite TRN-000971

2.3.3. Exploratory Endpoints

- Absolute change and relative change from baseline in LFC by Magnetic Resonance Imaging (MRI) Proton Density Fat Fraction (PDFF)
- Proportion of patients achieving a $\geq 30\%$ relative decline from baseline in LFC by MRI-PDFF
- Absolute change and relative change from baseline in corrected T1 (cT1) by MRI
- Change and percent change from baseline in select liver function tests: ALT, aspartate transaminase (AST), and gamma-glutamyl transpeptidase (GGT)
- Change and percent change from baseline in plasma PD biomarkers including fibroblast growth factor-19 (FGF19), 7α -hydroxy-4-cholest-3-one (7α C4), [REDACTED]
[REDACTED]
- Change and percent change from baseline in NASH and fibrosis blood biomarkers including cytokeratin-18 (CK-18) (M30 and M65), procollagen III n-terminal propeptide (PIIINP), tissue inhibitor of metalloproteinases-1 (TIMP-1), hyaluronic acid (HA), pro-peptide of type III collagen (Pro-C3) and calculated Enhanced Liver Fibrosis (ELF), Fibrosis-4 (FIB-4) and Nonalcoholic Fatty Liver Disease (NAFLD) fibrosis scores
- [REDACTED]
[REDACTED]

4. GENERAL STATISTICAL METHODS

4.1. Reporting Conventions

Individual patient data obtained from electronic case report forms (eCRFs), central laboratories, external sources, and any derived data will be presented in data listings by patient. The primary data source will be used for all analyses. All data listings that contain an evaluation date will contain a relative study day. Pre-treatment and on-treatment study days are numbered relative to the day of the first dose of study drug which is designated as Day 1. The preceding day is Day 1, the day before that is Day 2, etc.

All outputs will be incorporated into Microsoft Word rich text format (.rtf) files, sorted and labeled according to the International Council for Harmonisation (ICH) E3 guideline, E3

Structure and Content of Clinical Study Reports, and formatted to the appropriate page size(s), font type, and font size according to Food and Drug Administration (FDA) guidance of Portable Document Format Specifications.

For categorical variables, summary tabulations of the number and percentage of patients within each category of the parameter will be presented. Percentage calculations will be based on non-missing data, unless otherwise specified. If there are missing values, the number missing will be presented, but without a percentage. Percentages are rounded to 1 decimal place, unless otherwise specified.

For frequency counts of categorical variables, categories whose counts are zero will be displayed for the sake of completeness. For example, if none of the patients discontinue due to "Lost to Follow-up," this reason will be included in the table with a count of 0. Percentages will be presented to 1 decimal place, with the exception of 0, which will be presented without percent, and 100, which will be presented without decimal places. Values less than 0.1% will be presented as "<0.1%." Values less than 100% but greater than 99.9% will be presented as ">99.9%."

For continuous variables, the number of patients, mean, standard deviation (SD), median, 25th (Q1) and 75th (Q3) percentiles, minimum, and maximum values will be presented. The precision of summary statistics, unless otherwise specified will be as follows: mean, median, Q1, and Q3 to 1 more decimal place than the raw data, SD to 2 decimal places more than the raw data, and minimum and maximum to the same decimal places as the raw data. In general, the number of decimal places should not exceed 3 decimal places unless appropriate.

For log-normal data

[REDACTED] the geometric mean and geometric coefficient of variation (CV%) will also be presented. The precision of descriptive statistics will be as follows: mean, median, Q1, and Q3 to 1 more decimal place than the raw data, SD to 2 decimal places more than the raw data, the minimum and maximum to the same number of decimal places as the raw data, geometric mean to 3 significant figures, and geometric CV% to 1 decimal place.

[REDACTED]

Confidence intervals (CIs) will be provided and will be rounded to 1 decimal place, unless otherwise specified, in the table and listing shell. A full set of summary statistics will only be presented if there are 3 or more values available. If there are less than 3 values, only the min, max, and N will be presented. The other summary statistics will be denoted as not calculated (NC).

For tables where rounding is required, rounding will be done to the nearest round-off unit. For example, when rounding to the nearest integer, values \geq XX.5 will be rounded up to XX+1 (e.g., 97.5 will round up to 98), while values <XX.5 will be rounded down to XX (e.g., 97.4 will round down to 97).

All statistical tests comparing groups will be conducted at the 2-sided, 0.05 level of significance, unless otherwise specified. Summary statistics for each treatment group will be presented, as well as two-sided 90% and 95% CIs comparing groups will be provided.

Other general programming specifications are provided in [Appendix 1](#).

4.2. Computing Environments

All descriptive statistical analyses will be performed using SAS software Version 9.4 or higher, unless otherwise noted.

Plasma PK [REDACTED] for TERN-101 will be estimated using non-compartmental methods with Phoenix WinNonlin® Version 8.3 or higher.

Medical history and AEs will be coded using Medical Dictionary for Regulatory Activities (MedDRA) version 23.0. Concomitant medications will be coded using World Health Organization Drug Dictionary (WHODD), B2 Enhanced March 2020.

Study Data Tabulation Model (SDTM) and Analysis Data Model (ADaM) datasets will be prepared using Clinical Data Interchange Standards Consortium (CDISC) SDTM Implementation Guide (IG) Version 3.3, ADaM Version 2.1, and CDISC ADaM IG Version 1.2 including most current occurrence and time to event IGs.

4.3. Partial Dates

Imputation of partial adverse event and concomitant medication dates are specified in [Appendix 2](#), respectively.

All data recorded on the case report form will be included in data listings.

4.4. Data Conventions

The precision of original measurements will be maintained in summaries, when possible.

Quantitative safety laboratory tests containing less than (<) and greater than (>) symbols are test results that are below and above quantifiable limits, respectively. In order to retain these values for analysis purpose, the following will be imputed and stored within the analysis datasets:

- For values with <, the imputed value will be the numeric portion $\times 0.9$.
- For values with >, the imputed value will be the numeric portion $\times 1.1$.

PK and PD imputation of values below the limitation of quantitation (BLQ) are specified in [Section 8.9.1](#) and [Section 8.10.1](#), respectively.

Variables with a non-normal distribution that impacts the interpretation or validity of the planned analysis may have a data transformation applied (e.g., ln, \log_{10}).

4.5. Standard Calculations

Variables requiring calculation will be derived using the following formulas:

- Days – A duration expressed in days between one date (*date1*) and another later date (*date2*) will be calculated using the following formulas:

duration in days = *date2* – *date1* + 1, where *date1* \geq first administration date

duration in days = *date2* – *date1*, where *date1* < first administration date

- Months – A duration expressed in months is calculated as the number of days divided by 30.4375
- Years – A duration expressed in years between one date (*date1*) and another date (*date2*) is calculated using the following formulas:
 - duration in years = $(date2 - date1 + 1)/365.25$, where $date1 \geq$ first administration date
 - duration in years = $(date2 - date1)/365.25$, where $date1 <$ first administration date
- Body Mass Index (BMI) – BMI is calculated using height (cm) and weight (kg) using the following formula:
$$BMI \text{ (kg/m}^2\text{)} = \text{weight (kg)} / ([\text{height (cm)} / 100]^2)$$
- Change (CHG; equivalent to absolute change for liver fat content [LFC]) – Change will be calculated as:
$$\text{Change} = \text{later value} - \text{earlier (i.e. baseline) value}$$
- Percent change (PCHG; equivalent to relative change for LFC) – Percent change will be calculated as:
$$\text{Percent change} = ([\text{Change}] / \text{earlier [i.e. baseline] value}) \times 100$$

